1. At the baseline visit, women will go through informed consent and review of study eligibility. Objectives of the study, participation requirements, eligibility inclusion and exclusion will be reviewed in detail. We will complete checklist of inclusion criteria. If these are not met, the woman is excluded from the study. If she meets inclusion criteria, a checklist of exclusion criteria will be reviewed. If any exclusions are met, the woman is excluded from the study. The consent form will be reviewed in detail. If the woman consents and signs all pages of the form, randomization follows.

Randomization will be done in a 1:1 allocation ratio between the treatment and placebo arms. A computer algorithm will assign participant based on random permuted blocks design with block size between 2-4. Each participant will have an assigned Study ID number that is linked to their random assignment. Two staff members will know the randomization allocation. One staff member will be in the Yale Investigational Drug

Services (IDS) and will not have any further part in the study. The second study unblinded study member will be [name], an experienced research nurse within the Maternal-Fetal Medicine division. Remote dispensing has been approved by [name] of the Yale IDS.

In order to improve patient recruitment, our office will perform remote dispensing as per ASHP guidelines (document included in IRB re-submission). This includes temperature monitoring to maintain room temperature at 20-25 degrees Celsius utilizing an approved temperature monitoring system and temperature logging. We will also maintain drug accountability logs. All logs and regulations are submitted as documents to this IRB.

Yale IDS will continue to compound our study medications and dispense pre-counted and bottled medications labeled with study participant ID number as per the randomization scheme. This randomization scheme is shared with our staff member, [name], who will dispense the pre-bottled study medications to study participants as per the study ID number. All allergies and co-morbidities will be verified by research staff. Labeling of medications will be performed by [name].

Based on the participant assignment, we will dispense enough medication for the rest of the pregnancy. The bottles of study medication are pre-packaged and identical in appearance.

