- Elevated blood pressure (At least 2 systolic BP 120-129 mm Hg within 1 year pre-pregnancy until 20 weeks gestational age on at least 2 separate healthcare encounters) or Stage 1 hypertension (At least 2 systolic BP 130-139 and/or diastolic BP 80-89 within 1 year pre-pregnancy until 20 weeks gestational age on at least 2 separate healthcare encounters)
- Speaks English or Spanish
- Informed and written consent
- Confirmed single live intrauterine pregnancy (confirmed by positive cardiac motion by transvaginal or transabdominal ultrasound)

Exclusion:

- Chronic hypertension
- Pre-gestational diabetes, defined as diabetes diagnosed prior to pregnancy (type 1, 1.5, or 2)
- Chronic renal disease
 - diagnosis of stage 1 chronic kidney disease or higher and/or GFR <60 mL/min with duration at least 3 months and/or history of kidney transplantation and/or undergoing peritoneal or hemodialysis
- Systemic lupus erythematosus
- Antiphospholipid antibody syndrome
 - diagnosis made by having 1 or more clinical criteria and 1 or more laboratory criteria

- Clinical criteria: venous thrombosis, arterial thrombosis, obstetric complications (3 or more unexplained consecutive spontaneous abortions <10 weeks gestation, 1 or more unexplained deaths of a morphologically normal fetus after 10 weeks gestation, 1 or more premature births before 34 weeks gestation attributable to placental insufficiency, including severe preeclampsia or fetal growth restriction)
- Laboratory criteria: lupus anticoagulant, anti-cardiolipin IgG or IgM with titer >99th percentile, anti-beta 2 glycoprotein IgG or IgM with titer >99th percentile. Laboratory result must be positive twice at least 12 weeks apart
- Multifetal gestation
- ≥ 20 weeks gestation at time of randomization based on American College of Obstetricians and Gynecologists dating criteria. Dating will be based on last menstrual period (LMP) if regular, sure LMP is available that agrees with ultrasound dating. Otherwise, earliest ultrasound will be used for dating purposes.
- Prior history of hypertensive disorder of pregnancy
- Current pregnancy with known chromosomal, genetic, major malformations or fetal demise, or planned termination of pregnancy
- Women with contraindications to taking aspirin (bleeding diathesis such as Von Willebrand's disease, peptic ulcer disease, aspirin hypersensitivity, nasal polyps, asthma with aspirin-induced bronchospasm, severe liver disease).

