- Concurrent participation in another study that influences risk of preeclampsia
- Women who do not plan to deliver within the YNHH system

Write here

9. How will **eligibility** be determined, and by whom? *Write here*

Eligibility will be determined by study personnel with human subject protection training and ability to randomize patients. Patients will be approached and asked about eligibility criteria utilizing a checklist. If any exclusion criteria are met, the patient will not be eligible to participate in the study.

An MFM or OBGYN attending will confirm that the woman has a single, live intrauterine pregnancy by transvaginal or transabdominal ultrasound as part of standard of care. This ultrasound typically occurs between 8-14 weeks gestational age. The results of this ultrasound will be recorded in the woman's electronic medical record and this documentation will serve to confirm that this eligibility criterion has been met.

Women will be deemed to have elevated blood pressure if they have at least 2 systolic blood pressure measurements of 120-129 mm Hg within 1 year prior to pregnancy until 20 weeks gestational age on at least 2 separate healthcare encounters. Women will be deemed to have stage 1 hypertension if they have had at least 2 systolic blood pressure measurements of 130-139 mm Hg and/or diastolic blood pressures of 80-89 mm Hg within 1 year prior to pregnancy until 20 weeks gestational age on at least 2 separate healthcare encounters.

Enrolled participants will be randomized after a single, live intrauterine pregnancy is determined by ultrasound. They must then be randomized prior to 20 weeks' gestation.

10. **Risks:** Describe the reasonably foreseeable risks, including risks to subject privacy, discomforts, or inconveniences associated with subjects participating in the research.

Risks of aspirin:

- Most common: stomach upset, heartburn, nausea, vomiting (likelihood: 1-3/100 people)

- Uncommon: Gastrointestinal bleeding (likelihood: 0.5-3/1,000 people)
- Rare but serious: Acute renal failure, hives or facial swelling (likelihood: 7-20/10,000 people), bleeding in the brain (likelihood: 4/10,000 people)
- Contraindicated in people with: bleeding disorders (such as Von Willebrand's Disease), peptic ulcer disease, nasal polyps, asthma with aspirin-induced bronchospasm, severe liver disease, and aspirin or salicylate allergy or hypersensitivity.

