2. **Background Information:** Provide a description of previous human use, known risks, and data addressing dosage(s), interval(s), route(s) of administration, and any other factors that might influence risks. If this is the first time this drug is being administered to humans, include relevant data on animal models.

Low-dose aspirin is safe for use in pregnancy. Multiple large cohort and case-control studies have not found an association with congenital defects, structural, or developmental anomalies in the fetus. Several randomized controlled trials including thousands of women have demonstrated no increase in adverse fetal outcomes in doses less than 150mg per day.^{1,3,6} A meta-analysis of 22 studies women demonstrated no increase in birth defects.⁴ Use in the third trimester does not cause premature closure of the ductus arteriosus.⁷

Maternal use is safe without an increased risk of bleeding. There is no increased risk of gastrointestinal bleeding, placental abruption, epidural hematoma, and postpartum hemorrhage.¹ This was determined by several meta-analyses including over 20,000 pregnant women.²

Low dose aspirin is recommended for use during pregnancy to reduce risk of developing preeclampsia in women with at least one high risk factor or at least two moderate risk factors for developing preeclampsia. This management plan is recommended by numerous sources, including the United States Preventive Task Forces and the American College of Obstetricians and Gynecologists.⁵ Aspirin will not be withheld from women who have indications for aspirin prophylaxis in pregnancy.

References:

1. CLASP Collaborative Group (1994). CLASP: a randomized trial of low-dose aspirin for the prevention and treatment of pre-eclampsia among 9364 pregnant women. *Lancet*, 343(8898):619-629
3. Golding J (1998). A randomized trial of low dose aspirin for primiparae in pregnancy: the Jamaica low dose aspirin study. *British Journal of Obstetrics and Gynecology*, 105:293-299
4. Kozer E et al (2002). Aspirin consumption during the first trimester of pregnancy and congenital anomalies: a meta-analysis. *American Journal of Obstetrics and Gynecology*, 187(6): 1623-1630

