- The aspirin and placebo tablets expire after 6 months. These expiration dates are clearly labeled and discussed with the patient.

- *Unused study medication is collected at the completion of the study (after delivery of their baby) and returned to IDS*

Check applicable Investigational Drug Service utilized:

YNHH IDS CMHC Pharmacy West Haven VA

PET Center None

Other:

Note: If the YNHH IDS (or comparable service at CMHC or WHVA) will not be utilized, explain in detail how the PI will oversee these aspects of drug accountability, storage, and preparation.

2. Use of Placebo: Not applicable to this research project

If use of a placebo is planned, provide a justification which addresses the following:

- Describe the safety and efficacy of other available therapies. If there are no other available therapies, state this.
No other available therapies.
- State the maximum total length of time a participant may receive placebo while on the study.
Total length is from randomization until delivery (maximum 36 weeks). Aspirin will not be withheld from patients that would have otherwise received it as part of the standard of care were they not in this study. Women with any single high-risk factor or 2+ moderate risk factors will be offered aspirin as part of their clinical care and are not included in this study; this study only enrolls women with elevated blood pressure or stage 1 hypertension +/- only one other moderate risk factor.
- Address the greatest potential harm that may come to a participant as a result of receiving placebo.
Greatest harm would be hypersensitivity to any included ingredient in the placebo
- Describe the procedures that are in place to safeguard participants receiving placebo.
Use of Yale IDS for preparation of placebo
Data Safety Monitoring Committee will review both the aspirin and placebo arms for any adverse events

3. Continuation of Drug Therapy After Study Closure Not applicable to this project

Are subjects provided the opportunity to continue to receive the study drug(s) after the study has ended?

Yes If yes, describe the conditions under which continued access to study drug(s) may apply as well as conditions for termination of such access. *Write here*

NO If no, explain why this is acceptable.

Use of low dose aspirin is beneficial during pregnancy to reduce the risk of preeclampsia. The American College of Obstetricians and Gynecologists does not currently endorse postpartum use.

B. DEVICES

N/A

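### The placebo justification says women with two or more moderate risk factors are outside the study, but the eligibility lists do not exclude them

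*Combined protocol and SAP*

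**What the plan says.** Section II, B, Use of Placebo, treats one high-risk factor as enough to keep a woman out of the trial, and sets a threshold for moderate factors too: those with "2+ moderate risk factors will be offered aspirin as part of their clinical care and are not included in this study". It then describes the population: "this study only enrolls women with elevated blood pressure or stage 1 hypertension +/- only one other moderate risk factor".

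Section II, B, Background Information, describes low-dose aspirin as recommended for "women with at least one high risk factor or at least two moderate risk factors for developing preeclampsia", attributes this to national bodies, and adds: "Aspirin will not be withheld from women who have indications for aspirin prophylaxis in pregnancy".

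Section I, 8 is the operative list. Its inclusion items cover age, singleton pregnancy, blood pressure, language, consent and a live intrauterine pregnancy. Its exclusions name individual high-risk conditions, for example "Prior history of hypertensive disorder of pregnancy". They also cover gestational age, fetal conditions, contraindications to aspirin, other studies and delivery site.

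Section I, 9 applies these criteria by checklist: "If any exclusion criteria are met, the patient will not be eligible to participate in the study". Section I, 4 has staff complete an inclusion checklist and then an exclusion checklist, after which: "If the woman consents and signs all pages of the form, randomization follows". Allocation is 1:1.

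**The concern.** The protocol defends placebo partly by saying that women for whom it describes aspirin as recommended care are not in the trial. That protection works only if something at screening keeps them out. The high-risk half of the statement has counterparts among the exclusions. The moderate-factor half has none.

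Two things are at stake. The main one is the placebo justification itself, because a woman it places outside the study can be assigned placebo by staff who follow the listed criteria correctly. The secondary one is the treatment contrast. If providers prescribe open-label aspirin to some of these women, the difference between arms shrinks.

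**Working it through.** **Comparing the texts**

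| Place | Rule on two or more moderate factors | Rule on aspirin indicated or in use |
|---|---|---|
| Section II, B, Use of Placebo | Not included; at most one *other* moderate factor | Not withheld where standard of care would give it |
| Section II, B, Background Information | Given as an indication for aspirin | Not withheld where indicated |
| Section I, 6 Subject Population | None | None |
| Section I, 8 inclusion list | None | None |
| Section I, 8 exclusion list | None | None (contraindications only) |
| Section I, 9 eligibility process | None | None |

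Three other passages might close the gap, but none does:

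- Section III, 5 describes a record review for medical eligibility before approach. It does not define the term, and the in-person step that follows confirms the eligibility criteria, which leads back to the same lists.
- Section I, 4 has staff verify co-morbidities. This sits in the dispensing text and states no moderate-factor rule.
- The safeguards for placebo participants in Use of Placebo are preparation by the pharmacy service and a safety review: "Data Safety Monitoring Committee will review both the aspirin and placebo arms for any adverse events". Neither acts on who is enrolled.

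**Can the rule be applied as worded?** The protocol does not list the moderate factors; they may be meant by reference to the national recommendations. The word *other* leaves it open whether the qualifying blood pressure counts. If it does not, the two parts of the sentence agree. If it does, a woman allowed one other factor already has two.

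**Number of women.** The documents give no prevalence, so 2%, 5% and 10% are assumptions.

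- Randomised: 466 × 0.02 = 9.3; 466 × 0.05 = 23.3; 466 × 0.10 = 46.6.
- On placebo: 233 × 0.02 = 4.7; 233 × 0.05 = 11.7; 233 × 0.10 = 23.3.

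**Dilution (illustration only).** Inputs from Section I, 13: 29% on placebo, 18% on aspirin, alpha 0.05, 80% power, 233 per arm. Sidedness is not stated; two-sided is assumed.

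The plan's figure first, with variance pooled under the null and p̄ = 0.235:

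n = [1.960 √(2 × 0.235 × 0.765) + 0.842 √(0.29 × 0.71 + 0.18 × 0.82)]² / 0.11² ≈ 232.1, rounded up to 233 per arm, 466 in total. This matches the protocol.

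Let d be the share of the placebo arm taking open-label aspirin with the full planned effect. That is d = (share with two or more moderate factors) × (share of those taking aspirin). These women are given the average 29% risk. The placebo rate becomes 0.29 − 0.11d, and

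power = Φ{[Δ√233 − 1.960 √(2p̄(1−p̄))] / √(p₁(1−p₁) + p₂(1−p₂))}

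where p₁ is the diluted placebo rate, p₂ = 0.18, Δ = p₁ − p₂ and p̄ is the mean of the two.

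| d | Arises from | Placebo rate | Power |
|---|---|---|---|
| 0 | no drop-in | 29.0% | 80.2% |
| 0.01 | half of 2% | 28.89% | 79.4% |
| 0.02 | all of 2% | 28.78% | 78.7% |
| 0.025 | half of 5% | 28.725% | 78.3% |
| 0.05 | all of 5%, or half of 10% | 28.45% | 76.3% |
| 0.10 | all of 10% | 27.9% | 72.1% |

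**The case against.** The best reply is that the protocol should be read as a whole. Use of Placebo is part of it and is worded as a rule, and nothing in Section I, 8 permits what that rule forbids. On this view, enrolling such a woman would be a protocol deviation and the defect is one uncopied sentence. The checklist form is not in the documents and may carry the item. That much stands: actual practice cannot be seen. But the protocol makes the listed criteria the route to randomisation, and a rule found only in the drug section's placebo answer is not among them.

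A second reply is that routine prenatal care continues under the woman's own provider (Section I, 4) and aspirin is not to be withheld, so a woman on placebo is not formally denied it. This is true, and it means harm would need both screening and the provider's offer to fail. These are commitments, though, without a screening step. Participants are also blinded and are given a list of salicylate-containing products to avoid (Section I, 11), which may work against the provider's offer.

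Third, the two harms cannot both be counted for one woman: if she takes open-label aspirin she dilutes the contrast, and if she does not she causes no dilution. This is right, and dilution is treated here as secondary. The power figures rest wholly on assumed inputs and the losses at 2% or 5% are small.

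Finally, the natural reading of *other* may be that blood pressure does not count. That reading makes the sentence consistent, but the text should say so.

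**Conclusion.** The concern holds. The criteria that lead to randomisation do not contain a restriction on which the placebo justification relies. Following the lists as written can put on placebo a woman the protocol says is not included. This must be fixed, and the reason is that inconsistency alone, not any loss of power.

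The textual gap is certain. Its effect on enrolment is unknown: no misenrolment is shown and no prevalence is given. If 2% to 10% of women had two or more moderate factors, about 5 to 23 of the 233 on placebo would be affected. If half to all of those took fully effective open-label aspirin, power would fall from 80.2% to between 79.4% and 72.1%. The planned sample size of 466 is not disputed.

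**What to change.** - **Reconcile the texts.** Make Section I, 8 and 9, the screening checklist, and Background Information and Use of Placebo in Section II, B state one rule. It should name the moderate factors, say how the qualifying blood pressure counts, and say whether aspirin already prescribed or in use affects eligibility. Which rule to adopt is for the sponsor.
- **Count those affected.** Report, by arm, any women already randomised who meet one version of the rule but not the other. They stay in the intention-to-treat analysis.
- **Report open-label aspirin by arm**, from the medications abstracted at chart review (Section I, 4).

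The cost is one protocol and checklist amendment and perhaps slower screening. The count needs a review of moderate-factor data. The medical and family history and medication list in Section IV may supply part of it, but whether more abstraction is needed cannot be known until the factors are named. The open-label report uses data already being collected.

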The patient and the rest of the research staff personnel are blinded to study allocation. The staff members who are unblinded will not be involved in data acquisition, statistical analysis, and paper writing. Yale IDS will dispense study medication at the time of randomization. Yale IDS will perform pill counting at the beginning and completion of study enrollment in order to assess patient adherence with the regimen. Medication adherence may be encouraged by helping participants to set a daily reminder on their phone or calendar.

2. Participants will be contacted by telephone **1 week** after randomization. The purpose of this visit is to ensure the participant has received study medication and initiated the regimen. We will then discuss any side effects, questions, and/or concerns about the study. Any problems will be discussed and mitigated if possible.

[figure not shown]
3. The third encounter will be 6 weeks (+/- 1 week) after randomization in person to coincide with routine prenatal visit or via telephone. The purpose of this study visit is to review their pregnancy course, use of study medications, any side effects, difficulties with the study, and have opportunities to make comments and/or ask questions. The participants will be asked to bring their study medication for pill count at the time of this encounter, if the study visit is able to be performed in person. Study participants will continue their routine prenatal care with pregnancy management performed routinely per their provider.

4. The fourth encounter will be 16 weeks (+/- 1 week) after randomization in person to coincide with routine prenatal visit or via telephone. If the participant is already delivered by this time, the visit will be performed via telephone postpartum. The purpose of this study visit is to review their pregnancy course, use of study medications, any side effects, difficulties with the study, and have opportunities to make comments and/or ask questions. The participants will be asked to bring their study medication for pill count at the time of this encounter, if the study visit is able to be performed in person.

5. The rest of the study will be conducted via chart review. Each prenatal visit will be reviewed for blood pressure, evaluation of symptoms, review of any laboratory and/or imaging results. New diagnoses, medications, and hospital admissions will be documented.

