An independent data safety monitoring board will be constructed, consisting of three members outside of Yale University who are not co-investigators on the trial. Two of these members will be obstetricians and one a biostatistician.

Either the principal investigator or the IRB have the authority to stop or suspend the study or require modifications.

2. The risks associated with the current study are deemed greater than minimal for the following reasons:

1. We do not view the risks associated with the experimental arm as minimal risks.

Although we have assessed the proposed study as one of greater than minimal risk, the potential exists for anticipated and/or unanticipated adverse events, serious or otherwise, to occur since it is not possible to predict with certainty the absolute risk in any given individual or in advance of first-hand experience with the proposed study methods. Therefore, we provide a plan for monitoring the data and safety of the proposed study as follows:

3. Attribution of Adverse Events:

Adverse events will be monitored for each subject participating in the study and attributed to the study procedures / design by the principal investigator and [name] according to the following categories:

- a.) Definite: Adverse event is clearly related to investigational procedures(s)/agent(s).
- b.) Probable: Adverse event is likely related to investigational procedures(s)/agent(s).
- c.) Possible: Adverse event may be related to investigational procedures(s)/agent(s).
- d.) Unlikely: Adverse event is likely not to be related to the investigational procedures(s)/agent(s).
- e.) Unrelated: Adverse event is clearly not related to investigational procedures(s)/agent(s).

4. Plan for Grading Adverse Events:

The following scale will be used in grading the severity of adverse events noted during the study:

1. Mild adverse event
2. Moderate adverse event
3. Severe

5. Plan for Determining Seriousness of Adverse Events:

Serious Adverse Events:

In addition to grading the adverse event, the PI will determine whether the adverse event meets the criteria for a Serious Adverse Event (SAE). An adverse event is considered serious if it results in any of the following outcomes:

1. Death;
2. A life-threatening experience in-patient hospitalization or prolongation of existing hospitalization;
3. A persistent or significant disability or incapacity;
4. A congenital anomaly or birth defect; OR

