There may be reduction in rates of hypertensive disorders of pregnancy (gestational hypertension, preeclampsia, HELLP syndrome, eclampsia) both to study participants and future pregnant women with elevated BP and stage 1 hypertension.

SECTION VI: RESEARCH ALTERNATIVES AND ECONOMIC CONSIDERATIONS

1. **Alternatives:** What other alternatives are available to the study subjects outside of the research?

If women do not want to participate in the study, they will continue routine prenatal care.

2. **Payments for Participation (Economic Considerations):** Describe any payments that will be made to subjects, the amount and schedule of payments, and the conditions for receiving this compensation.

N/A

3. **Costs for Participation (Economic Considerations):** Clearly describe the subject's costs associated with participation in the research, and the interventions or procedures of the study that will be provided at no cost to subjects.

There are no costs to study participants. Study medications (whether low dose aspirin or placebo) will be provided at no cost. No further interventions or procedures will be required.

4. **In Case of Injury:** This section is required for any research involving more than minimal risk, and for minimal risk research that presents the potential for physical harm (e.g., research involving blood draws).

a. Will medical treatment be available if research-related injury occurs?

Medical treatment will not be available from research staff.

b. Where and from whom may treatment be obtained?

Medical treatment will be through the participant's usual provider, emergency room, and any other health professionals as needed.

c. Are there any limits to the treatment being provided?

No.

d. Who will pay for this treatment?

Insurance will be billed for any treatment and the participants will be responsible for any co-pays required by the insurance company for standard treatment.

e. How will the medical treatment be accessed by subjects?

If needed, medical treatment will be sought through usual avenues—either through the patient's usual healthcare provider (whether obstetrician or primary care physician) or emergency department. Participants will be asked to report any side effects of study medication (whether aspirin or placebo). If any side effects are reported, research personnel will encourage and help set up medical diagnosis and treatment services.

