During the study visits (whether conducted in person or by telephone), we will ask women questions about their blood pressure and symptoms of preeclampsia. If any study participant notes onset of preeclampsia symptoms (headache, vision changes, right upper quadrant pain, and/or dyspnea) or new onset of systolic blood pressure ≥ 140 mm Hg and/or diastolic blood pressure ≥ 90 mm Hg, she will be asked to contact her primary obstetrician immediately.

IMPORTANT REMINDERS

Will this study have a billable service? Yes No

A billable service is defined as any service rendered to a study subject that, if he/she was not on a study, would normally generate a bill from either Yale-New Haven Hospital or Yale Medical Group to the patient or the patient's insurer. The service may or may not be performed by the research staff on your study, but may be provided by professionals within either Yale-New Haven Hospital or Yale Medical Group (examples include x-rays, MRIs, CT scans, specimens sent to central labs, or specimens sent to pathology). Notes: 1. There is no distinction made whether the service is paid for by the subject or their insurance (Standard of Care) or by the study's funding mechanism (Research Sponsored). 2. This generally includes new services or orders placed in EPIC for research subjects.

If answered, "yes", this study will need to be set up in OnCore, Yale's clinical research management system, for Epic to appropriately route research related charges. Please contact [contact]

Are there any procedures involved in this protocol that will be performed at YNHH or one of its affiliated entities?

Yes No

If Yes, please answer questions a through c and note instructions below.

a. Does your YNHH privilege delineation currently include the **specific procedure** that you will perform? Yes No

b. Will you be using any new equipment or equipment that you have not used in the past for this procedure? Yes No

c. Will a novel approach using existing equipment be applied? Yes No

If you answered "no" to question 4a, or "yes" to question 4b or c, please contact the YNHH Department of Physician Services ([name]) for prior approval before commencing with your research protocol.

IMPORTANT REMINDER ABOUT RESEARCH AT YNHH

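### Direct questions about harm at the study contacts are framed only as side effects, so mild symptoms a woman does not link to the capsule, and no provider charts, may never reach the investigator's attribution step

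*Combined protocol and SAP*

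**What the plan says.** Section I, 4 (Research Plan) sets three contacts after randomization. At the 1-week call staff check that the capsules have arrived and been started, and the text continues: "We will then discuss any side effects, questions, and/or concerns about the study". At 6 and 16 weeks the purpose is to "review their pregnancy course, use of study medications, any side effects, difficulties with the study", with room for comments and questions. Section VI, 4e, which deals with how treatment for a research injury is reached, says: "Participants will be asked to report any side effects of study medication (whether aspirin or placebo". The same item states that at study visits "we will ask women questions about their blood pressure and symptoms of preeclampsia", and it names four of those symptoms.

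Two further sentences in Section I, 4 do not depend on the woman's view of cause: "Each prenatal visit will be reviewed for blood pressure, evaluation of symptoms, review of any laboratory and/or imaging results" and "New diagnoses, medications, and hospital admissions will be documented". Item 6 there adds review of the mother's outpatient, emergency and hospital records for a year after delivery.

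Section I, 12, item 3 states: "Adverse events will be monitored for each subject participating in the study and attributed to the study procedures / design by the principal investigator". A colleague shares that task, and the scale has five levels, from definite to unrelated. Items 4 and 5 grade severity and define seriousness; neither defines an adverse event. Section I, 10 gives the leading aspirin harms: "Most common: stomach upset, heartburn, nausea, vomiting (likelihood: 1-3/100 people".

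**The concern.** An attribution scale that includes unlikely and unrelated works as intended when events are collected first and judged afterwards. Asking about side effects invites the woman to make that judgement herself. She is blinded, and the commonest harms in Section I, 10 are complaints she could reasonably put down to pregnancy. (That overlap is an inference; the documents do not state it.) None of these harms is named for active enquiry, although Section VI, 4e does name preeclampsia symptoms.

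What is at stake is the completeness of the mild-symptom data. These feed the investigator's assessment of how frequent and severe adverse events are (Section I, 12, item 7) and the safety committee's look at both arms (Section II, B, Use of Placebo).

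**Working it through.** **Step 1. Set the collection routes side by side.** The test case is a woman with mild heartburn who does not suspect the capsule.

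- *1-week call.* Asks about side effects, plus questions and concerns about the study. Pregnancy course is not mentioned. The symptom may not come up.
- *6- and 16-week contacts.* Pregnancy course is reviewed as well as side effects. The symptom may be mentioned, but nothing prompts for it.
- *Section VI, 4e.* Asks for side effects of the study medication, so the causal link is explicit. The symptoms named for enquiry are those of preeclampsia; none is gastrointestinal or a bleeding symptom.
- *Chart review.* Covers symptoms at each prenatal visit, diagnoses, medications and admissions, whatever the cause. It finds the symptom only if she mentioned it and the provider wrote it down.
- *Diaries and questionnaires.* Listed in Section IV, item 1; their content is not described.

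A serious or medically attended event is reached through the chart. A mild symptom that is neither volunteered nor charted can miss every route.

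**Step 2. Arm size.** Section I, 13 gives 29% against 18%, 80% power, alpha 0.05 and 233 per arm. With a two-sided test, pooled variance and no continuity correction:

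n = [1.960 × √(2 × 0.235 × 0.765) + 0.842 × √(0.29 × 0.71 + 0.18 × 0.82)]² / 0.11² = 232.04, rounded up to 233.

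The plan's 466 is reproduced. It is not in dispute and serves here only as the denominator.

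**Step 3. Women affected on aspirin, before any loss.** From Section I, 10:

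- 0.01 × 233 = 2.33
- 0.03 × 233 = 6.99

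So about 2.3 to 7.0 women. This is a rate in people taking aspirin, not an excess over placebo.

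**Step 4. What equal loss does.** Let a share f of symptoms be captured in each arm, with true rates p1 on aspirin and p0 on placebo.

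- Observed risk ratio: (f × p1)/(f × p0) = p1/p0, unchanged.
- Observed difference: f × (p1 − p0), reduced in proportion to f.

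**Step 5. Illustration of the loss of precision.** The documents give neither f nor a placebo rate, so both are assumed, as is a 3-point excess on aspirin. The power formula matches Step 2, with 233 per arm.

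| Assumed placebo rate | True rates | Power, f = 1 | Observed rates, f = 0.5 | Power, f = 0.5 |
|---|---|---|---|---|
| 5% | 8% v 5% | about 26% | 4% v 2.5% | about 15% |
| 20% | 23% v 20% | about 12% | 11.5% v 10% | about 7.5% |

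Power is low even with full capture; incomplete capture lowers it further.

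**The case against.** The strongest reply has four parts.

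*The wording is a lay summary, not a script.* The form asks for non-technical language in Section I, 4, and side effects may be shorthand there for adverse events. No interview script or case report form is shown. This stands in part: what staff will actually say is unknown. The plan as written still offers no neutral question, no definition of an adverse event and no symptom list.

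*The explicit causal wording is in the wrong place to carry the point.* Section VI, 4e concerns access to treatment. This stands. The point rests on the contacts in Section I, 4, with 4e as support.

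*Other routes exist.* A reader might infer that women are never asked about general health, or that the participant's guess takes over from the investigator's assessment. The documents support neither. Pregnancy course is reviewed at two contacts, charts are read for symptoms as well as diagnoses, and Section I, 12 does not limit adverse events to what women call side effects. What remains is mild or moderate symptoms outside medical care.

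*More questions bring more noise.* At a fixed excess, a higher background lowers power: about 26% at 5% and 12% at 20% in the illustration. This stands for a pooled count of all complaints. It has less force if named symptoms are tabulated separately, and for a given symptom full capture gave higher power than half capture in both rows.

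**Conclusion.** The point holds in a limited form. The direct harm questions are framed as side effects, so some mild or moderate symptoms may be filtered by the woman's own view of cause before the investigator sees them. Serious and medically attended events are reasonably covered.

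The pool at issue is about 2.3 to 7.0 women on aspirin, if the protocol's 1 to 3 per 100 applies to this population. How many would be missed cannot be derived from the documents.

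Three stronger readings are tempting and unsupported:

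- That these harms will be under-reported: no figure shows it, so the claim is that they may be.
- That the comparison would favour one arm: participants and all but two staff are blinded, so similar proportional loss is the natural expectation. That leaves the risk ratio unchanged and reduces the absolute difference and the precision.
- That the 1 to 3 per 100, scaled by a capture rate, gives a lost excess over placebo: it is a rate on aspirin, and any capture rate is assumed.

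The primary outcome and the sample size are unaffected. This is a cheap improvement to safety data collection.

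**What to change.** In Section I, 4, at the 1-, 6- and 16-week contacts and in both arms:

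1. Open with a neutral question about any new or worse health problem since the last contact.
2. Follow with a short fixed checklist taken from Section I, 10: stomach upset; heartburn; nausea or vomiting; any bleeding; hives or facial swelling.
3. Record every positive answer regardless of cause, keeping checklist items as separate fields.
4. Only then apply the attribution scale of Section I, 12, item 3.

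State in Section I, 12 that an adverse event is recorded irrespective of presumed cause, and align the wording of Section VI, 4e.

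This needs a reworded contact script and one added form. It adds no visit and does not change the sample size. The downside is more minor events, probably mostly unrelated, to log and attribute.
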